4.3. Symptomatic nausea and vomiting without delayed gastric emptying

Patients will qualify for enrollment in this category if they meet all the criteria for gastroparesis defined above with the exception of a normal scintigraphic gastric emptying and no other cause found. Many patients present with symptoms similar to those of gastroparesis but exhibit normal scintigraphic gastric emptying of a solid meal. This disorder has previously been defined by the Rome II consensus criteria as "functional" vomiting. Many of these individuals satisfy the Rome III definitions of chronic idiopathic nausea or functional vomiting.

4.4. Target composition

It is expected that 80% of patients will meet the definition of gastroparesis as above with delayed gastric emptying. We will cap the number of the patients with symptomatic nausea and vomiting without delayed gastric emptying (as described in section 4.3 above) to 20%. Patients will be recruited predominantly from outpatient clinics either in gastroenterology, diabetes or primary care settings. Inpatients with the diagnosis of gastroparesis may also be invited to participate once they are discharged from the hospital and more stable medically.

Gastroparesis Registry Protocol

5. Screening and enrollment

5.1. Inclusion criteria

- Symptoms of gastroparesis of at least 12 weeks duration (do not have to be contiguous) with varying degrees of nausea, vomiting, abdominal pain, early satiety, post-prandial fullness,
- Completion of a 4-hour scintigraphic low fat Egg Beaters gastric emptying study
 - Patients with either or both abnormal 2 hour (>60% retention) and 4 hour (>10% retention) gastric emptying will be enrolled and classified as definite gastroparesis (Gp)
 - Patients with normal gastric emptying, but with symptoms of gastroparesis may be enrolled and classified as possible gastroparesis or gastroparesis-like with normal gastric emptying (GLNGE)
- Age at least 18 years at initial screening visit
- Ability and willingness to participate in follow-up

5.2. Exclusion criteria

- Inability to comply with or complete the gastric emptying scintigraphy
- Presence of other conditions that could explain the patient's symptoms:
 - Pyloric or intestinal obstruction
 - Active inflammatory bowel disease
 - Eosinophilic gastroenteritis
 - Neurological conditions such as increased intracranial pressure, space occupying or inflammatory/infectious lesions
 - Acute liver failure
 - Advanced liver disease (Child's B or C; a Child-Pugh-Turcotte (CPT) score of 7 or greater)
 - Acute renal failure
 - Untreated chronic renal failure (serum creatinine >3 mg/dL)
- Total or subtotal gastric resection (patients with prior fundoplication or postvagotomy gastroparesis after pyloroplasty or antrectomy with Billroth I, Billroth II, or Roux-en-Y gastrojejunostomy will be eligible for enrollment)
- Any other plausible structural or metabolic cause
- Any other condition, which in the opinion of the investigator would interfere with study requirements
- Inability to obtain informed consent

5. Screening and enrollment

Clinical centers must be certified by the Data Coordinating Center to start enrollment in the Gastroparesis Registry. Prior to implementation of this protocol, the principal investigator must have the protocol and consent form approved by the Institutional Review Board for Human Research (IRB) at his/her institution. Once a candidate for Gastroparesis Registry has been identified, details will be carefully discussed with the patient. The patient will be asked to read and sign the consent form that was approved by the IRB. There will be a separate consent for the collection, storage, and use of DNA for genetic research.

6. Schedule of visits and procedures

Screening, consent, and follow-up overview: Many of the Gastroparesis Registry (GpR) patients will likely come from the current patient rosters of the GpCRC investigators and new patients referred to them for evaluation and treatment of gastroparesis. Patients may be referred from physicians outside the Consortium and some patients may refer themselves to be included in the Registry. Patients considered by the clinical center investigator as likely to be eligible for enrollment in the Registry may be consented and screened at a visit that is part of the ongoing clinical care of the patient. Tests may be ordered and billed to insurance to appropriately complete the evaluation of the disease and general medical condition according to a reasonable standard of care. Patients who are thought to be eligible will be invited to screen for enrollment in the Registry. Screening may take place over several visits. At the initial screening visit, the details of Registry participation will be introduced. If the patient is agreeable and is judged to have definite or possible gastroparesis, then he/she may enter the formal screening phase. Screening will include both prospective and retrospective data collection. Prospective data collection will be carried out by completion of forms and questionnaires by patients and by performance of various laboratory tests and clinical procedures on patients. Retrospective data collection will be carried out by review of the patient's medical chart and abstraction of various data elements. Abstracted data may include laboratory and radiology test results.

The screening visits may occur on separate calendar days and may occur over a period of up to 16 weeks. The data collected at these visits and during the retrospective chart review are used to determine eligibility and to establish baseline values. Consent for screening and HIPAA authorization to disclose protected health information with the Gastroparesis Registry must be obtained from the patient prior to initiating any data collection for the Gastroparesis Registry; this consent and authorization must be obtained at the start of the initial screening visit. The consent will include consent for screening and enrollment in the Registry, including follow-up.

The currently projected maximum follow-up on a patient entered into the Gastroparesis Registry will be approximately 4 years. Data will be collected during screening visits to establish baseline values, and then every 16 weeks after enrollment if the patient does not return in the interval for exacerbation of gastroparesis symptoms. If this happens, an interim visit will be keyed in the database to reflect the exacerbation of symptoms. The Appendix 10.2 displays the consent and data collection schedule for screening, enrollment, and follow-up.

6.1. Screening visits

Formal screening begins once the patient has signed the HIPAA authorization and consent for screening and enrollment in the Gastroparesis Registry (GpR). The patient is considered to be registered once the consent is signed. Recording of data on GpR baseline data collection forms may begin once this initial consent and authorization are obtained.

The purpose of the screening visits is to initiate collection of the baseline data needed to determine eligibility. Activities at screening visits include:

- Signature on the Gastroparesis Registry consent form
- Signature on Gastroparesis Registry HIPAA authorization form
- Assignment of GpCRC patient identification number
- Medical/medication history
- Physical examination including vital signs, height, weight, anthropometric measurements
- Review status of laboratory tests including those reflecting glycemic control
- Review status of gastrointestinal tests including endoscopy and X-rays
- Review status of gastric emptying scintigraphy
- Patient to sign medical records release to obtain prior reports
- Patient to provide location/contact information
- Obtain retrospective health history information/materials relevant to study eligibility
- Clinical center coordinator to register patient on clinic data system
- Clinical center coordinator to request prior reports from health care provider
- Questionnaires (PAGI-SYM, PAGI-QOL, Rome III questionnaires, health related quality of life, brief pain inventory, IDIOMS, Block food questionnaire, Beck Depression Inventory, State Trait Anxiety Inventory, and others to be specified).

During the screening visits, the patient completes the questionnaires needed for enrollment in the Gastroparesis Registry and has blood drawn for additional research protocol related laboratory tests and specimen (plasma, serum, and DNA) banking. The patient must attend the screening visit after an overnight fast at least 8 hours and should be instructed to bring a snack to be eaten after fasting blood is drawn. Standards of care for patients with gastroparesis are described in the Gastroparesis Registry Standard Operating Procedures (SOP) Part IV. Other procedures at screening visits include:

- Hematology
- Clinical chemistry
- HbA1c
- Liver panel
- Serology (ANA, Scl-70, CRP, SPEP, Sed rate)
- Fasting blood for plasma and serum banking
- Blood draw for DNA banking (no fasting required)

Gastric emptying scintigraphy: To enter the Gastroparesis Registry with a diagnosis of definite gastroparesis (see section 4.1 for definition), the patient must have a 4 hour scintigraphic evaluation of gastric emptying using a low fat Egg Beaters meal that is available for review by the GpCRC investigator who must confirm that the patient meets the criteria for definite gastroparesis. This may be repeated as part of standard of care for diagnosis or follow-up as determined by the clinical center investigator during screening. The gastric emptying scintigraphy may have been obtained at any time within 6 months prior to enrollment.

6.2. Follow-up visits

Gastroparesis Registry follow-up visits will be scheduled every 16 weeks after enrollment. The date of enrollment will be the date from which the follow-up visits are timed (i.e., the zero time). Each follow-up visit will have a time window around the target date for the visit; the time window is an interval of days during which the visit may be completed, and the data collected at the visit may be used to fulfill the data collection requirements for the visit. Data collected outside the allowable time window for a visit are not useable as data for the visit. Each visit has an ideal date for the visit, a lower window date (opening date for the window) and an upper window date (closing date for the window). The dates for a specific patient are specified on the visit time windows schedule for the patient. This schedule is generated by the clinic data system when a patient is enrolled in the Gastroparesis Registry.

Procedures and forms to be completed at each of the follow-up visits are:

- 16, 32, 48, 64, 80, 96, 112, 128, 144, 160, 176, 192 weeks visit
 - Follow-up medical history (medication changes/additions, symptom exacerbations or interventions, surgeries, hospital admissions, new diagnoses of co-morbidities, complications of interventions such as infections)
 - Physical examination
 - Laboratory data (hematology, clinical chemistry, HbA1c, liver panel) as indicated
 - HbA1c values should be obtained at each follow-up visit for patients with diabetes
 - Various questionnaires such as PAGI-SYM, PAGI-QOL, brief pain inventory, IDIOMS, and others to be specified
 - Rome III questionnaires, Block food questionnaire, health related quality of life, Beck Depression Inventory, State Trait Anxiety Inventory (only at 48, 96, 144, 192 weeks)
 - Blood collection for plasma and serum banking (only at 48, 96, 144, 192 weeks)
 - Laboratory data for ANA, Scl-70, CRP, SPEP, sedimentation rate as indicated
 - Documentation of any additional GI tests performed as part of standard of care

Separate entries will be made in the Gastroparesis Registry data system for symptom flares requiring medical intervention.

6.3. Data form contents

Baseline medical history. The Gastroparesis Registry (GpR) forms will capture the following:

- Demographics
- Onset and duration of symptoms
- Nature and severity of symptoms
- Other GI symptoms particularly chronic pancreatitis
- Presence of diabetes (including gestational diabetes)
- If so, onset, type, glycemic control, other system involvement (eye, kidney, heart, peripheral and autonomic neuropathy)
- Presence of "overlap" symptoms
- Results from upper GI endoscopy performed within 12 months prior to enrollment

GPCRC\Gpr\RegProt\Manall_30 9:14 am Tuesday, December 1, 2009/klc

- Results from gastric emptying test performed within 6 months prior to enrollment
- Other medical problems particularly any history of connective tissue disorder
- Family history of GI or related illness
- Past medical/surgical events and illness history

Baseline medication history. The GpR forms will capture all prescription medications taken within 6 months prior to enrollment. These should include medications taken for the treatment of gastroparesis, pain (visceral or somatic) and any others. GpR forms will also include information on use of alternative therapies, antioxidants, vitamins, and/or other dietary supplements. Any known medication allergies will be documented.

Physical examination. Initial exam will include:

- Vital signs: Temperature, pulse, blood pressure
- Anthropometrics: Height, weight (without shoes or heavy clothing)
- Laboratory items: All laboratory items listed may be obtained as archival material from the patient's chart or should be collected as part of the standard of care. Maximum acceptable intervals between the date of collection of laboratory results and GpR registration (date of initial screening visit) will be specified in the data collection form. The draw date of the laboratory test must be recorded on the data form.
- Hematology: Hemoglobin, hematocrit, white blood cell count (WBC), platelet count, prothrombin time (PT), partial thromboplastin time (PTT)
- Clinical chemistry and HbA1c: Creatinine, total protein and albumin, sodium, potassium, chloride, bicarbonate, calcium, BUN, glucose and HbA1c.
- Liver panel: Total bilirubin, aspartate aminotransferase (AST), alanine aminotransferase (ALT), alkaline phosphatase
- Screening etiologic tests: Anti-nuclear antibody (ANA), scleroderma antibody (Scl-70), C-reactive protein (CRP), serum protein electrophoresis (SPEP), sedimentation rate

Follow-up medical history. Follow-up health history will include data on symptom severity, medication changes, additions; key events or interventions, surgeries, hospital admissions; new diagnoses of co-morbidities; complications of diabetes such as retinopathy, neuropathy, nephropathy, cardiovascular events.

6.4. Plasma, serum, and DNA for banking

Fasting plasma, serum and DNA will be banked for specific Gastroparesis Registry research questions and other GpCRC ancillary studies. Blood will be drawn at the screening/enrollment visit and yearly thereafter on all patients enrolled in the Gastroparesis Registry. Standardized methods for plasma, serum, and DNA processing that allow for maximal preservation of banked specimens and storage in designated -70 degrees C freezers will be applied across all clinical centers or at the NIDDK central repositories (see Gastroparesis Registry Standard Operating Procedures (SOP) I: Clinical Center Operations).

7. Statistical and design considerations

The Gastroparesis Registry is the first prospective, multi-center, observational study with standardized collection of data on a large cohort of patients with gastroparesis or gastroparesis-like symptoms. The overall objective is to compile patient data and specimens to clarify the epidemiology, etiology, and natural history of gastroparesis. The Registry will also be used as a resource for recruitment of patients into randomized, controlled, clinical trials of treatments for gastroparesis. The recruitment goal is up to 700 patients with gastroparesis from 1-4 years of follow-up on each patient.

As the first large study of gastroparesis, the objectives and hypotheses to be examined are intentionally very broad (see Section 2). As the study progresses, additional questions may arise that can be addressed through data or specimens collected for the Registry.

Addressing the specified hypotheses of the Gastroparesis Registry will require the full gamut of statistical analysis procedures, from survival analysis to ROC curves. Nearly all questions will require identification of appropriate subgroups of patients from all clinical centers contributing to the Gastroparesis Registry with analyses tailored to the hypothesis to be addressed.

This process will be accomplished through formal publication proposals corresponding to each hypothesis prepared by members of the GpCRC and approved by the full GpCRC Steering Committee. The DSMB will review approved proposals to ensure that the studies are consistent with the goals of the GpCRC and will periodically monitor progress on these publications. Each of these proposals must include a statistical plan and sample size justification prepared by the Data Coordinating Center. Each proposal must contain the following information:

- Statement of the hypothesis to be addressed
- Specification of the primary comparison groups appropriate for the hypotheses
- Specification of the primary and secondary outcome variables
- Specification of inclusion/exclusion criteria needed to define the subgroup of Registry patients needed for the hypothesis
- Specification of baseline covariates or methods to be used to select the covariates for adjustment of comparisons among the primary comparison groups
- Specification of methods for dealing with missing values or lost to follow-up
- Specification of primary and confirmatory analytic methods to be used

The sample size must be justified by calculations (using nQuery Advisor or similar software), which will include a Type I error of 0.05 or less, a power of 0.80 or higher, specification of a clinically meaningful effect size, and estimated event rates or estimates of variability (eg, SD of primary outcome measure), and a rationale for achievement of the sample size in a reasonable period of time, either from existing patients in the Registry or from patients to be recruited in the future, or both, and, if appropriate, adjustments for missing data. Adjustments to Type I errors for multiplicity of comparisons are not needed for hypotheses pre-specified in Section 2.1. Other hypotheses, that are

not pre-specified and that arise as a result of data analyses, will be identified in publications as exploratory and needing further confirmatory data.

Since the Gastroparesis Registry will generate longitudinal data over time, analytic methods must account for, as applicable, time to events, repeated measurements, counts, or other discrete responses. For time to event data, we will use the Cox proportional hazards regression model with covariates tailored to the hypothesis under investigation. For hypotheses involving repeated measurements, events, counts or other discrete responses, we will use either of two approaches: (1) generalized linear models with generalized estimating equations (GEE) with robust variance estimation to account for the clustering; or, (2) multilevel generalized linear mixed models with random coefficients to account for within patient clustering as well as other sources of variations like clinic effects.

8. Human subjects issues

The study protocol, consent forms, and data collection forms will be submitted to each clinical center's IRB and to the DCC's IRB. Additionally, each clinical center will submit to their IRB any recruitment materials to be used at their site. A site may not initiate any patient contact about the Gastroparesis Registry until the site has IRB approval and the DCC has certified the site for initiation of patient activities. Consent forms must have IRB approval. Sites must provide the DCC with copies of the initial IRB approval notice and subsequent renewals, as well as copies of the IRB approved consent statements. All study personnel will have completed training in the Protection of Human Subjects per NIH guidelines.

The proposed study anticipates recruiting a significant proportion of racial/ethnic minorities (Black or African American, Hispanics or Latino, Asian, American Indian/Alaska Native, Native Hawaiian or other Pacific Islander) as well as non-Hispanic white subjects. We anticipate that the patients recruited from diverse sources, including community and tertiary referral populations, will capture the entire spectrum of gastroparesis.

All subjects enrolled in the Gastroparesis Registry will receive a standard of care for gastroparesis and identified associated medical problems as defined by the GpCRC Steering Committee (see SOP IV: Standards of Care for Patients with Gastroparesis). This will include provision of health care counseling and educational materials at enrollment and on an ongoing basis during follow-up.

Prototype consents will be prepared for the study. Individual sites may add material but may not delete material thought to be necessary for informed consent. Sites may reformat and reword information to conform to their local requirements. A signed consent form will be obtained from the subject. The consent form will describe the purpose of the study, the procedures to be followed, and the risks and benefits of participation. A copy of the consent form will be given to the subject and this fact will be documented in the subject's record.

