- Beck Depression Inventory
- State Trait Anxiety Inventory
- Rome III questionnaires
- Survival at the end of study period

Sample size

- Separately justified for each hypothesis
- Specification of primary outcome measure for hypothesis
- Type I error ≤ 0.05 and power ≥ 0.80
- Specification of primary comparison groups
- Specification of minimum clinically meaningful effect size for the primary outcome
- Specification of method for handling missing data
- No adjustments for multiplicity of comparisons

1. Background and rationale

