2.1. Hypotheses to be tested

The major broad hypotheses that will be tested using the GpR as a primary tool are as follows:

- A grading system (mild, compensated, chronic failure) for gastroparesis can be developed that predicts the subsequent clinical course of patients.
- Most patients with gastroparesis have a disease course with episodes of exacerbations.
- The delay in gastric emptying predicts the clinical course of patients with gastroparesis.
- Delayed gastric emptying is linked to greater impairment in quality of life, increased economic cost, increased healthcare utilization, and worse clinical outcomes.
- Profound delays in solid food gastric emptying (e.g. less than 10% emptied at 2 hours or less than 25% emptied at 4 hours) relate to symptoms, whereas mild delays (e.g. 25- 50% emptied at 2 hours or 50-90% emptied at 4 hours) have no correlation with symptoms.
- Markedly accelerated early emptying (more than 75% emptied at 1 hour) relates to symptoms, whereas mildly accelerated emptying (50-75% emptied at 1 hour) has no correlation with symptoms.
- Weight loss in gastroparesis correlates with reduced fasting ghrelin levels.

Confidential, not for citation or attribution

5

- The clinical course of gastroparesis will vary by diagnostic categories such as diabetic, idiopathic, and post-surgical: (1) Diabetic gastroparesis will be related to the clinical course of a patient's diabetes mellitus and autonomic nervous system (ANS) neuropathy; (2) Post-infectious idiopathic gastroparesis will be different from other types of idiopathic gastroparesis.
- The survival outcomes of gastroparesis will vary by diagnostic categories such as diabetic, idiopathic, and post-surgical: Diabetic gastroparesis patients may have a shorter survival compared to other diagnostic categories.
- Symptom progression in diabetic gastroparesis relates to worsening autonomic dysfunction, dysrhythmias, fundic relaxation impairment, and visceral hyperalgesia.
- Control of gastropathy symptoms in diabetes (as opposed to improved emptying) leads to better glycemic control (decreased hemoglobin A1c).
- Patients with type 1 diabetes mellitus and type 2 diabetes mellitus with HbA1c greater than 8.5%, 7.5 to 8.5% and 6.5 to 7.5% will have different upper GI symptoms, different gastric dysrhythmias and different rates of gastric emptying.

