- The clinical course of idiopathic gastroparesis patients with positive autoimmune markers will differ from patients without the autoimmune markers.
- Symptom resolution in postviral gastroparesis relates to improved gastric emptying, gastric dysrhythmias, fundic accommodation, visceral hyperalgesia.
- Symptoms in postfundoplication gastroparesis show improvement over the first 2 post-operative years that does not relate to improved vagal function (i.e. non-vagal pathways are recruited).
- Severe abdominal pain is infrequently the predominant symptom in patients with gastroparesis.
- Lifetime stressful events and a history of abuse relate to symptom severity in gastroparesis.
- Symptoms of gastroparesis fluctuate over time and worsen in the last half of the menstrual cycle.
- A subset of patients with gastroparesis have evidence of an inflammatory process. These patients have a slow downhill course.
- Nausea, but not vomiting or abdominal pain, is associated with the decreased quality of life in patients with gastroparesis.
- Specific genetic markers can be identified in patients with familial forms of gastroparesis.
- A heritable component of gastroparesis is detectable in patients with type 2 diabetes mellitus.
- Associated phenomena such as autonomic neuropathy or dysmotility of other gastrointestinal regions are important in determining the natural history and clinical outcomes in patients with gastroparesis.
- A subset of patients with gastroparesis will also have subtle or overt dysmotility of the small and/or large intestine which will adversely impact prognosis.
- Patients with type 2 diabetes mellitus have high prevalence of upper GI symptoms, gastric dysrhythmias, and gastroparesis (comparable to literature for patients with type 1 diabetes mellitus).

3. Scientific background

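### Section 7 waives multiplicity control for every Section 2.1 hypothesis, but Section 2.1 fixes topics rather than tests, and one of them is an open genetic-marker search

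*Protocol*

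**What the plan says.** The rule appears twice. Section 7 says: "Adjustments to Type I errors for multiplicity of comparisons are not needed for hypotheses pre-specified in Section 2.1". The sample-size part of the design synopsis says: "No adjustments for multiplicity of comparisons", with no restriction to Section 2.1.

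Section 7 then sets out how other hypotheses are treated. Those "not pre-specified and that arise as a result of data analyses, will be identified in publications as exploratory and needing further confirmatory data". No such label is required for a Section 2.1 item.

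Section 2.1 introduces its list with "The major broad hypotheses that will be tested using the GpR as a primary tool are as follows". It has 25 bullets. Those that matter here are:

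- Genetic markers: "Specific genetic markers can be identified in patients with familial forms of gastroparesis". No marker, gene, panel or number of markers is given.
- HbA1c bands in type 1 and type 2 diabetes: patients in three bands "will have different upper GI symptoms, different gastric dysrhythmias and different rates of gastric emptying", which is three outcome domains.
- Delayed emptying: one item ties it to four outcomes (quality of life, cost, healthcare use, clinical outcome).
- Symptom progression in diabetic gastroparesis and symptom resolution in postviral gastroparesis: four mechanisms each.

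Each hypothesis is to be worked out in a publication proposal that names comparison groups, primary and secondary outcomes and analytic methods. Its sample-size calculation must be one "which will include a Type I error of 0.05 or less, a power of 0.80 or higher". The Steering Committee approves the proposal and the DSMB reviews it.

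**The concern.** Pre-specification is a good reason not to adjust when it fixes the test: one outcome, one comparison, one analysis. Section 2.1 fixes the subject of the test and leaves outcomes, contrasts and markers to later proposals. Section 7 lets those proposals draw on patients already in the Registry, so the tests may be chosen after data exist.

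The marker item shows the problem most clearly. A search over unnamed markers is multiple testing by construction, yet it falls under the waiver because its topic is on the list. A marker reaching 0.05 could be reported as pre-specified, with neither an adjusted threshold nor a statement that confirmation is needed. A hypothesis left off the list but raised by the data would have to carry that statement.

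The Registry describes itself as the first large study of the disease and expects its results to support genomic work and later trials. Chance findings without a caution attached could misdirect that work.

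**Working it through.** The protocol gives no familywise error rate, so there is no stated figure to reproduce. The check is what the waiver permits.

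**Inputs**

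- Per-test level 0.05: the upper limit in Section 7 and in the synopsis ("Type I error ≤ 0.05 and power ≥ 0.80").
- Four components: from the delayed-emptying item and from each of the two mechanism items in Section 2.1.
- Number of markers: not in the protocol. 100 is assumed, and 1,000 is shown for range.
- All nulls true and tests independent: assumptions.

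**Formulas**, for k tests at level 0.05

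- Chance of at least one false positive: 1 − 0.95^k
- Expected false positives: 0.05 × k
- Bonferroni level: 0.05 / k

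**Results**

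| Case | k | At least one false positive | Expected | Bonferroni level |
|---|---|---|---|---|
| Four-component item, any one counts | 4 | 1 − 0.95^4 = 18.5% | 0.20 | 0.0125 |
| 100 markers (assumed) | 100 | 1 − 0.95^100 = 99.4% | 5 | 0.0005 |
| 1,000 markers (assumed) | 1,000 | about 100% | 50 | 0.00005 |

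Positive correlation among the tests would lower the third column but not the fourth.

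**If all components must succeed.** When an item counts as supported only if every component is significant, testing each at 0.05 keeps the error for the item at or below 0.05. The 18.5% applies only where any single component is enough.

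**Cost of adjusting**, two-sided, 80% power, normal approximation. The detectable effect is proportional to z(1 − α/2) + z(0.80).

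- α = 0.05: 1.960 + 0.842 = 2.802
- α = 0.0125 (four components): 2.498 + 0.842 = 3.339; ratio 3.339 / 2.802 = 1.19
- α = 0.0005 (100 markers): 3.481 + 0.842 = 4.322; ratio 4.322 / 2.802 = 1.54

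At fixed sample size the detectable effect is thus 19% larger for four components and 54% larger for 100 markers.

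**The case against.** The best defence has four parts.

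1. **The proposal process.** Each hypothesis gets a statistical plan from the Data Coordinating Center, named primary outcomes and groups, and two layers of review. Within-item structure is what such a plan would normally settle, and a level below 0.05 is allowed. This is a real partial safeguard. But no listed proposal element requires error control across outcomes, contrasts or markers, the number of primary outcomes is not limited to one in Section 7, and the same section tells the authors that adjustment is not needed.

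2. **Separate questions in an observational registry need no joint adjustment.** This stands. A reader might infer from the 25 bullets that the whole list should share one error rate (25 single tests would give 1 − 0.95^25 = 72%). That is not the defect. The questions are distinct, and several bullets are descriptive rather than null-hypothesis tests.

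3. **Compound items may be conjunctions.** The HbA1c and delayed-emptying items join their parts with *and*, and can be read as requiring all of them. On that reading nothing is inflated. The protocol does not say which reading applies. It is also tempting to count 18 HbA1c tests (3 domains × 2 types × 3 pairwise contrasts) and quote 1 − 0.95^18 = 60%. The pairwise contrasts within a set of three groups are correlated. With equal groups a set has 12.2% rather than 14.3%, so six independent sets give 1 − (1 − 0.122)^6 = 54%, and correlated domains would give less. The count itself depends on how the item is read.

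4. **Genetics may be left to ancillary studies under their own protocols.** This weakens the point without removing it. The marker item is on the list of hypotheses for which the Registry is the primary tool, and Section 6.4 banks DNA for Registry questions as well as ancillary ones. No genotyping platform is described, so a genome-wide marker count has no basis in the text.

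**Conclusion.** The point holds in a limited form. Section 7 and the synopsis lay down a rule that is too wide: it waives adjustment for a whole topic list when only a fixed test would justify the waiver. This is a rule the protocol states, not detail left for an analysis plan.

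The marker item is the clear case: 5 expected false hits and a 99.4% chance of at least one at an assumed 100 markers, with independent true nulls. For compound items the size is modest and conditional: 18.5% for four components, if any one counts as success and the tests are independent.

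A reader might infer that such findings will be published as confirmed. The protocol never says so. It only omits the exploratory label for Section 2.1 items, so the supported statement is that they could be presented as pre-specified without that caution. Nor does the Type I error requirement amount to a broken familywise guarantee; it is an input to each proposal's sample-size calculation.

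**What to change.** Reword Section 7, and the synopsis line to match, as follows.

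- The waiver covers one primary test for each Section 2.1 hypothesis: one named outcome and one comparison, fixed in the approved proposal.
- For the genetic-marker item, require familywise or false-discovery control over all markers tested.
- For items where any one of several outcomes, strata or mechanisms would count as success, either control error within the item or label the non-primary components exploratory.
- State that no adjustment is needed where all components must succeed, for a heritability test on a single parameter, or across separate hypotheses.

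No new data or visits are needed. The cost in sensitivity is not trivial: at 80% power and fixed sample size, the detectable effect rises about 54% under Bonferroni over 100 markers. That matters in a registry of up to 700 patients analysed largely in subgroups. For compound items the cost (about 19% for four components under Bonferroni) can be avoided by using the exploratory label instead.
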